1.1.3. SPR720

Spero is developing SPR720 as an oral therapy for the treatment of patients with NTM-PD caused by MAC. SPR720 is a chemically stable phosphate prodrug that converts rapidly to SPR719, the active moiety, in vivo.

SPR719 was identified and optimized through structure-guided design and iterative structure-activity relationship studies; it is an aminobenzimidazole, a novel class of antibacterial agents that target the ATPase subunits of gyrase and, when present, topoisomerase. These enzymes are highly conserved and essential in bacteria for DNA replication (Locher et al 2015). In mycobacteria, only gyrase enzymes have been identified. The potent enzyme activity demonstrated by SPR719 translates to growth inhibition of a range of pathogens such as *Mycobacterium tuberculosis* (Locher et al 2015; O'Dowd et al 2015) and nontuberculosis mycobacteria such as MAC, *M. abscessus* complex, and *M. kansasii*, including isolates that are resistant to the current SOC agents amikacin, clarithromycin, and, importantly, the fluoroquinolones (Brown-Elliott et al 2018).

1.1.3.1. SPR720 Nonclinical Development

Nonclinical studies conducted to date on SPR720 and/or its active moiety SPR719 have demonstrated acceptable safety and pharmacokinetic (PK) profiles. No adverse effect levels identified in repeat-dose toxicity studies of SPR720 in rats and in monkeys provide exposure multiples to the anticipated human therapeutic exposure, and, in rats, SPR720 was determined to be nongenotoxic. In safety pharmacology studies in vitro and in monkeys and rats, SPR720 and/or its active moiety SPR719 exhibited no adverse effects on the normal functioning of the cardiovascular, respiratory, or central nervous systems.

1.1.4. SPR720 Clinical Development

Spero has completed a single Phase 1 study in the United Kingdom in healthy volunteers to assess the safety, tolerability, and PK of SPR720 (Study SPR720-101). A comprehensive set of nonclinical studies has also been completed that evaluated the PK/metabolism, safety pharmacology, and toxicity of SPR720 (prodrug) and SPR719 (active moiety).

The advancement of SPR720 into the Phase 1 clinical assessment was based on a favorable profile exhibited in a suite of preclinical in vitro and in vivo safety, toxicology, absorption, distribution, metabolism, and excretion studies, as well as its demonstration of

potency in vitro and in vivo activity versus multiple, clinically important species of NTM, including MAC and *M. abscessus*.

1.2. Risks and Benefits

SPR720 has demonstrated in vitro and in vivo biological activity against a range of NTM species, including MAC, the most common pathogen group in NTM-PD, and *M. abscessus*, a highly resistant organism associated with a high rate of mortality.

The collective preclinical data to date suggests that SPR720 has an acceptable safety profile, encouraging target pathogen efficacy, drug distribution to key sites of infection such as the lung, and a wide therapeutic margin.

SPR720 has been successfully evaluated in a single-ascending-dose/multiple-ascending-dose Phase 1 study in humans (Study SPR720-101). SPR720 was safe and well tolerated in healthy volunteers at doses believed to be in the therapeutic range for up to 14 days of dosing. The safety, tolerability, and PK data from this Phase 1 study further support a favorable risk-benefit profile for SPR720.

SPR720 is a novel agent with the potential to be the first oral antibiotic designed to treat NTM disease, a rare orphan disease.

2. STUDY OBJECTIVES

2.1. Primary Objective

The primary objective of this study is to evaluate the PK of SPR719 generated from the orally (po) administered SPR720 prodrug in a patient population with NTM-PD.

2.2. Secondary Objective

The secondary objective of this study is to evaluate the safety and tolerability of SPR720 in a patient population with NTM-PD.

[REDACTED]

3. INVESTIGATIONAL PLAN

3.1. Overall Study Design and Plan

This is a Phase 2a, multicenter, randomized, partially blinded, placebo- and comparator-controlled study to evaluate the safety, tolerability, PK, and efficacy of 2 dose levels of SPR720 compared with placebo or SOC for the treatment of patients with NTM-PD due to MAC. The SPR720 and placebo arms will be double blinded, and the SOC arm will be open label.

Approximately 90 male and female patients 18 years of age and older with a diagnosis of NTM-PD due to MAC will be enrolled and treated for 28 days. Treatment-naïve patients must be ready to initiate treatment within the next 3 months. Patients who have received prior treatment may be eligible if they have culture evidence of persistent, recurrent, or relapsed disease; have been off therapy for at least 6 months; and are likely to reinitiate or resume treatment.

For the sparse PK sites, enrolled patients will be randomly assigned 5:5:5:4 (Arm 1: Arm 2: Arm 3: Arm 4) into one of the following treatment arms until 72 patients are enrolled (19 to 20 patients each for Treatment Arms 1, 2, and 3 and 15 to 16 patients for Arm 4). For the intense PK sites, enrolled patients will be randomly assigned 1:1:1 (Arm 1: Arm 2: Arm 3) into one of the following treatment arms (6 patients each for Treatment Arms 1, 2, and 3):

- **Treatment Arm 1: SPR720 Low Dose:** Double-blinded SPR720 investigational product (IP) 500 mg once daily for 28 days.
- **Treatment Arm 2: SPR720 High Dose:** Double-blinded SPR720 IP 1000 mg once daily for 28 days.
- **Treatment Arm 3: Placebo:** Double-blinded placebo once daily for 28 days.
- **Treatment Arm 4: SOC:** At Investigator's discretion. Recommended as follows: 2-drug or 3-drug SOC, including clarithromycin 500 to 1000 mg PLUS ethambutol hydrochloride (HCl) approximately 15 mg/kg or azithromycin 250 to 500 mg once daily PLUS ethambutol HCl approximately 15 mg/kg once daily for 28 days. Optional rifampin 600 mg or rifabutin 300 mg once daily for up to 28 days may be added to the SOC regimen.

Inform the medical monitor of alternative SOC regimens and discuss concerns or questions.

Randomization will be stratified by diagnosis at enrollment as either 1) nodular-bronchiectatic or 2) fibro-cavitary NTM-PD.

Clinic study visits will occur on Days 1, 7, 14, 21, and 28 (end-of-treatment [EOT] visit) (± 1 day). Patients in the double-blinded Treatment Arms 1, 2, and 3 will be evaluated in a follow-up visit on Day 56 (± 2 days) (28 days after EOT). Patients in the open-label SOC Treatment Arm 4 will be discontinued from the study after the EOT visit.

Baseline symptoms will include chronic cough, fatigue, frequent throat clearing, dyspnea, hemoptysis, excessive mucus (sputum) production, fever, night sweats, loss of appetite, unintended weight loss, wheezing, and chest pain. A multi-dimensional patient-reported outcome (PRO) (see [Appendix 3](#)) instrument assessing severity and changes in these baseline symptoms

will be administered at clinic visits on Days 1, 7, 14, 21, and 28 in all arms and Day 56 in Treatment Arms 1, 2, and 3.

Patient-collected pooled expectorated sputum will be collected on Days –1, 6, 13, 20, and 27 (i.e., the day before clinical study visits over an approximate 24-hour [h] period) for all patients and, for patients in Treatment Arms 1, 2, and 3, on Day 55 (i.e., the day before the follow-up visit on Day 56). In all cases, the patient-collected sputum will be collected on the day before the actual clinic visit. Sputum will also be collected at each clinic visit using a standard induction protocol.

[figure not shown]
Patients in Treatment Arms 1, 2, and 3 will participate in the collection of blood samples for PK analysis as follows:

- At least 3 selected qualifying sites will enroll a total of at least 18 patients (at least 6 per treatment arm) for intensive PK evaluation. On Days 1 and 28, blood samples for intense PK will be collected at pre-dose and post-dose: 1 h, 2 h, 4 h, 8 h, 12 h, and 24 h. On Days 7, 14, and 21, blood samples will be obtained at: pre-dose, 1 h post-dose, and just before discharge from the clinic. The acceptable windows for PK collection are specified in the Schedule of Assessments ([Table 2](#)).
- At all remaining, samples will be collected for sparse PK evaluation, on Days 1, 7, 14, 21, and 28. Blood samples will be obtained at pre-dose, 1 h post-dose, and just before discharge from the clinic.
- Patients randomized to the SOC arm will not participate in PK collection.

Actual dates and times of blood samples as well as dates and times of study drug administration will be recorded. Please refer to the Schedule of Assessments ([Table 2](#)) for allowable windows.

A diagram of the study design is presented in [Figure 1](#).

Figure 1: Study Design

Abbreviations: DB=double-blinded; EOT=end of treatment; HCl=hydrochloride; OL=open label; QD=once daily; SOC=standard of care.

3.2. Study Duration

Patients will be screened within 42 days prior to the first dose of study drug. All patients will be treated for 28 days. Patients in Treatment Arms 1, 2, and 3, only, will have a follow-up visit 28 days after the completion of therapy. The maximum duration of participation for each patient will be approximately 98 days (including a 42-day screening period, 28-day treatment period, and 28-day follow-up period) for Treatment Arms 1, 2, and 3, and approximately 70 days (including a 42-day screening period and 28-day treatment period) for Treatment Arm 4 SOC recipients.

3.3. Selection of Study Population

Approximately 90 male and female patients, 18 years of age and older, with a diagnosis of NTM-PD due to MAC will be enrolled in the study.

Specific entry criteria are detailed in [Section 3.3.1](#) and [Section 3.3.2](#).

3.3.1. Inclusion Criteria

Patients meeting all the following inclusion criteria should be considered for admission to the study:

1. Provided written informed consent
2. Male or female, 18 years of age or older at the time of consent
3. Has a diagnosis of NTM-PD due to MAC
4. Had at least 1 prior positive culture (sputum or bronchoalveolar lavage) positive for MAC in the previous 6 months
5. Has an induced sputum culture at screening positive for MAC by at least one of the following methods performed by the microbiology laboratory: quantitative culture on solid agar or growth on liquid media (MGIT)
6. Is either treatment naïve and has not received any prior treatment for MAC, OR if previously treated for MAC, has culture evidence of persistent, recurrent, or relapsed disease and has been off therapy for at least 6 months
7. In the opinion of the Investigator, is ready to initiate treatment (treatment naïve) or reinstate treatment (previously treated) within the next 3 months, and for whom a delay, in order to participate in a placebo-controlled clinical trial, is considered reasonable and clinically acceptable
8. Had clinical signs and symptoms within the 6 weeks before the date of consent that are consistent with NTM-PD with at least two of the following:
 - a. chronic cough
 - b. fatigue
 - c. frequent throat clearing
 - d. shortness of breath (dyspnea)
 - e. coughing up of blood (hemoptysis)

- f. excessive mucus (sputum) production
 - g. fever
 - h. night sweats
 - i. loss of appetite
 - j. unintended weight loss
 - k. wheezing
 - l. chest pain
9. Has a measured forced expiratory volume in 1 second (% predicted FEV1) $\geq 30\%$ on pulmonary function test within 3 months prior to consent
 10. Has a chest radiograph (CXR) or computed tomography (CT) scan within 6 months prior to consent with findings consistent with NTM-PD. If no CXR or CT scan is available, a CXR or CT scan should be performed at screening to confirm eligibility.
 11. If female, is of nonchildbearing potential (e.g. postmenopausal as demonstrated by follicle-stimulating hormone or surgical sterilization, i.e., tubal ligation or hysterectomy), or if of childbearing potential, be willing to commit to either sexual abstinence or use of at least 2 medically accepted, effective methods of birth control in combination (e.g., condom, spermicidal gel, oral contraceptive, indwelling intrauterine device, hormonal implant/patch, injections, approved cervical ring) from consent through follow-up. Patients randomized to the SOC arm will be followed up until EOT
 12. If male, is willing not to donate sperm and, if engaging in sexual intercourse with a female partner who could become pregnant, a willingness to use a condom in addition to having his female partner use a highly effective method of birth control (such as an intrauterine device, diaphragm, oral contraceptives, injectable progesterone, subdermal implants, or a tubal ligation) from consent through follow-up. Patients randomized to the SOC arm will be followed up until EOT
 13. Is willing and able to comply with all study assessments and adhere to the protocol schedule

3.3.2. Exclusion Criteria

Patients meeting any of the following exclusion criteria will not be enrolled in the study:

1. In the opinion of the Investigator, is not a candidate for a 3-month delay in initiation of standard multidrug therapy in order to participate in a placebo-controlled clinical trial or observation (e.g., severe symptoms, extensive disease burden)
2. Has disseminated or extrapulmonary NTM
3. Has end-stage NTM-PD or treatment-refractory NTM-PD and is unlikely to respond to protocol-specified SOC treatment
4. Had isolation on sputum cultures of any species of *Mycobacterium* other than a species included in MAC within the past 6 months
5. Had prior isolation of MAC with macrolide resistance
6. Has active tuberculosis at the time of consent

7. Has received any systemic (oral or IV) or inhaled antibiotic with activity against MAC between consent and randomization
8. Has a potentially confounding underlying pulmonary disease, including but not limited to cystic fibrosis, active pulmonary malignancy (primary or metastatic), NTM-hypersensitivity disease pneumoconiosis, or another advanced lung disease with a % predicted FEV1 < 30%
9. Has a history of a positive test for HIV, known CD4 count < 200/mm³ within the last year before time of consent, or a diagnosis of AIDS
10. Has an immunodeficiency or an immunocompromised condition, including neutropenia (< 1000 neutrophils/mm³ obtained from the central laboratory at screening), hematologic malignancy, a history of hematopoietic stem cell transplant, a history of solid organ transplant, is receiving immunosuppressive therapy (e.g., cancer chemotherapy, monoclonal antibodies for autoimmune disease, or medications to prevent transplant rejection), and has had long-term use of systemic corticosteroids (e.g., ≥ 20 mg/day of prednisone or systemic equivalent for at least 2 weeks)
11. Has a history of known or suspected *C. diff* infection
12. Has a history of epilepsy or known seizure disorder (excluding a history of childhood febrile seizures)
13. Has hepatic impairment at screening, as evidenced by alanine aminotransferase (ALT) or aspartate aminotransferase (AST) > 2 × upper limit of normal (ULN) or total bilirubin > 1.5 × ULN, or clinical signs of cirrhosis or end-stage hepatic disease (e.g., ascites, hepatic encephalopathy)
14. Has renal impairment (creatinine clearance < 50 mL/min) or end-stage renal disease requiring hemodialysis or peritoneal dialysis
15. If female, is pregnant or breastfeeding
16. Has a corrected QT (QTc) interval on electrocardiogram (ECG) > 470 ms
17. Has consumed drugs or supplements that are strong cytochrome P450 (CYP)3A4 enzyme inducers or strong CYP3A4 inhibitors (see [Appendix 1](#)) within 4 weeks of randomization
18. Has consumed drugs or supplements that are substrates of the hepatic transporters OATP1B1 or OATP1B3 (see [Appendix 2](#)) within 1 week of randomization
19. Has a documented hypersensitivity reaction or anaphylaxis to SPR720 or any of the specified SOC medications
20. Has received any investigational medication in the year before the time of consent
21. Has any other condition or prior therapy, which, in the opinion of the Investigator, would make the patient unsuitable for this study, including compliance with all study assessments and adherence to the protocol schedule

Patients who are unable to comply with the requirements of the study or who in the opinion of the Investigator should not participate in the study are not eligible.

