1. INTRODUCTION

1.1. Background

1.1.1. Nontuberculous Mycobacterial Pulmonary Disease

Nontuberculous mycobacterial pulmonary disease (NTM-PD) is a chronic, progressive disease that occurs through inhalation of pathogenic mycobacteria from environmental sources, including aerosols from water and dust from soil (Falkinham 2015). The most commonly reported nontuberculous mycobacterial (NTM) species causing NTM-PD in the United States (US) and worldwide are *Mycobacterium avium* complex (MAC), which includes *Mycobacterium avium*, *Mycobacterium intracellulare*, *Mycobacterium chimaera* and several other species and subspecies, *Mycobacterium kansasii*, and *Mycobacterium abscessus* (Griffith et al 2007; Falkinham 2015; Haworth et al 2017).

Nontuberculous mycobacterial pulmonary disease predominantly occurs in patients with underlying lung disease, including chronic obstructive pulmonary disease and bronchiectasis, patients with cystic fibrosis, older males, and nonsmoking women over the age of 50 years without previously diagnosed lung disease (Lady Windermere syndrome). Development of NTM-PD is based on a variety of pathogen and host-specific factors for which the pathophysiology is poorly understood (Griffith et al 2007). Risk factors for disease include underlying immunodeficiency, treatment with antitumor necrosis factor agents, and exposure to environmental water sources (Griffith et al 2007; Henkle and Winthrop 2015; Adjemian et al 2017; Baldwin et al 2019). The natural history of this disease is varied based on pathogen and host factors, but 5-year mortality rates as high as 35% have been reported for *M. abscessus* pulmonary disease. Risk factors for progressive lung disease include infection with *M. abscessus*, the presence of cavitary lung disease, and low body weight/body mass index (Dhillon and Watanakunakorn 2000; Lam et al 2006; Griffith et al 2007; Gochi et al 2015).

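### Exclusion 4 does not reach a non-MAC mycobacterium grown only on lavage, although inclusion 4 accepts lavage as evidence of MAC

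*Combined protocol and SAP*

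**What the plan says.** Section 3.3.1 opens with "Patients meeting all the following inclusion criteria should be considered for admission to the study", so the inclusion criteria are cumulative. Three of them bear on the organism:

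- Inclusion 3: "Has a diagnosis of NTM-PD due to MAC".
- Inclusion 4: "Had at least 1 prior positive culture (sputum or bronchoalveolar lavage) positive for MAC in the previous 6 months".
- Inclusion 5: "Has an induced sputum culture at screening positive for MAC by at least one of the following methods performed by the microbiology laboratory", the methods being quantitative solid culture or growth in liquid medium.

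On the exclusion side (Section 3.3.2), criterion 4 reads "Had isolation on sputum cultures of any species of" *Mycobacterium* "other than a species included in MAC within the past 6 months". Criterion 5, on macrolide-resistant MAC, names no specimen. Criterion 6 is "Has active tuberculosis at the time of consent", also without a specimen limit. Criterion 21 and the closing sentence of the section leave other unsuitable patients to the investigator.

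The synopsis has the same specimen scope for inclusion 4 and exclusion 4 as the body.

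**The concern.** Both criteria draw on the patient's culture history over six months, but they admit different specimens. A single lavage report listing MAC and a second mycobacterium can be used for its first line and disregarded for its second. Exclusion 5, the next item in the list, has no specimen limit, so sputum-only is not a convention for isolation criteria in this protocol. The documents give no reason for the limit in exclusion 4.

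Three things are at stake:

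- **Population.** The trial is meant for pulmonary disease caused by MAC. Exclusion 4 is the mandatory rule that keeps out patients with another non-tuberculous species, and as worded it misses one route by which such a species is found.
- **Attribution.** Symptoms and culture findings in a co-infected patient cannot be assigned to MAC alone. The serum biomarker in the notes to Table 2 is described as detecting peptides specific to NTM, not to MAC, so it carries the same ambiguity.
- **Patient protection.** Section 1.1.2 says that treatment depends on the causative species and names *M. abscessus* and *M. kansasii* beside MAC. Section 1.2 describes *M. abscessus* as highly resistant and linked to high mortality. A placebo patient receives no active study drug for 28 days and is then followed to Day 56.

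**Working it through.** No arithmetic applies, and the plan states no figure on this point to reproduce. The check is to set the criteria side by side and trace a patient through them.

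**Scope of each culture criterion**

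| Criterion | Organism | Specimens that count | Look-back |
|---|---|---|---|
| Inclusion 4 | MAC | sputum or lavage | 6 months |
| Inclusion 5 | MAC | induced sputum only | screening |
| Exclusion 4 | any non-MAC *Mycobacterium* | sputum only | 6 months |
| Exclusion 5 | macrolide-resistant MAC | not limited | any prior |
| Exclusion 6 | active tuberculosis | not limited | at consent |

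**Trace.** Take a patient whose lavage within the last six months grew MAC and a second mycobacterium. Inclusion 4 is met by that lavage. What follows depends on the other results:

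1. Screening induced sputum grows MAC only, and no other sputum in the window grew a non-MAC species. Inclusion 5 is met and exclusion 4 is not triggered. If the second species is not tuberculous, no mandatory criterion removes the patient.
2. Screening sputum does not grow MAC. Inclusion 5 fails and the patient is not eligible.
3. Screening sputum, or any other sputum in the window, also grows the non-MAC species. Exclusion 4 applies.
4. The second organism is *M. tuberculosis* with active disease. Exclusion 6 applies.

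Only case 1 is open.

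**Do other criteria close case 1?**

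- Inclusion 3 requires MAC disease but does not say that MAC must be the only pathogen.
- Inclusion 7 and exclusion 1 ask the investigator whether delaying treatment is acceptable. They do not mention a second species.
- Exclusion 8 covers confounding lung disease. Its list is open-ended, but the examples do not include another mycobacterial infection.
- Exclusion 21 and the closing sentence of Section 3.3.2 rest on investigator opinion.

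Each of these could lead an investigator to decline the patient. None obliges it. With about 30 sites planned, such judgment need not be uniform.

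**The case against.** A reader might infer that a mixed lavage by itself gets a patient into the trial. The documents do not support that. Inclusion 5 is a separate requirement that lavage cannot meet, and the screening sample is itself a sputum culture, so a second species growing there is excluded. Enrolment also requires the investigator to pass the patient on inclusions 3 and 7 and exclusions 1, 8 and 21. This stands, and it confines the point to case 1.

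A reader might also try to size the harm from the five-year mortality quoted for *M. abscessus* in Section 1.1.1, or from one patient's share of a blinded arm. Neither works. The mortality figure concerns five years, not 56 days. It concerns one species, and it lies inside the range that Section 1.1.2 gives for NTM-PD in general, so it shows no added risk from co-infection. One patient's share of an arm is the same for any patient and says nothing about how often this one occurs.

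The impact on the trial's stated aims is limited. The primary objective is SPR719 pharmacokinetics, the secondary is safety, and Section 8.1.4 plans no formal hypothesis. Nothing shows that a second mycobacterium would alter the PK endpoints. The efficacy assessments are redacted and no micro-ITT definition is visible, so whether non-MAC isolates are dealt with there cannot be known.

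Finally, the contrast with exclusion 5 shows that specimen wording varies between criteria. It does not show that the sputum limit is accidental. That is fair, and the sponsor should state a reason if it was chosen.

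What remains is a mandatory rule with a gap that only discretion covers.

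**Conclusion.** The mismatch is real and appears in both the synopsis and the body. A non-tuberculous, non-MAC species isolated only on lavage in the past six months is not a mandatory exclusion, although the same lavage can count toward inclusion 4. Such a patient can be enrolled when the screening induced sputum grows MAC only, no other sputum in the window grew the second species, and the investigator does not exclude on judgment.

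The size cannot be given. The documents state neither how many patients have lavage cultures nor how often these are mixed. They also do not say how often one induced sputum would recover a second species found on lavage. My assumption is that few patients are affected. No PK result, power or error rate is shown to depend on the point. The harm is to the population definition, to attribution and to the protection of placebo patients. The correction is still worth making, because it is specific and cheap and concerns a rule the sponsor chose to make mandatory.

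**What to change.** Reconcile the specimen scope of exclusion 4 with that of inclusion 4, in Section 3.3.2 and in the synopsis. Non-MAC *Mycobacterium* isolated in the past six months on any available respiratory culture, whether sputum or bronchoalveolar lavage, would then count. If the sputum limit is deliberate, state the reason in the protocol.

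The change is a few words in an amendment and needs no new test or visit. It has two costs. A small number of patients with a non-MAC lavage isolate would no longer be eligible. Sites would also have to check any lavage reports that already exist. That check is additional work for patients who meet inclusion 4 on sputum, since nothing now requires their lavage results to be consulted.
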